Hypothesis 1: CV vs. WT will exhibit higher cortico-striatal and striato-limbic and intrastriatal RSFC (Figure 1B and C: Base) and report higher craving for MA at baseline.

SA 2: Determine the effect of *acute* oral MA or placebo (PBO) administration on the interaction of *htaar1* CV vs. WT genotype on RSFC, craving, cognitive control, attention and subjective experience in MUD.

Hypothesis 2: Acute MA administration will lower RSFC in both genotypes, with a blunted decrease in the CV group (Figure 1C: MA and PBO).

Hypothesis 3: The CV group will exhibit, compared to WT, blunted effect of MA administration on craving, subjective experience and tests of attention and cognitive control.

Experimental Design:

Recruitment: MUD and control subjects will be recruited by advertisement from VAPORHCS, OHSU, community assistance programs. Advertisements will also be posted online externally utilizing Craigslist, the VAPORHCS web page, the quarterly newsletter (Veteran Connection), the VA Facebook page OHSU's Research Opportunities pages, the OHSU website (MARC page or dedicated lab page), Indeed.com, Ziprecruiter, Google Jobs, Localwise.com, Skoll.org, and community news publications (Street Roots, Portland Mercury, Willamette Weekly and possibly others). Approved flyers will be distributed throughout the community (retail locations, community assistance programs, primary care clinics, emergency departments, dental clinics, community outreach programs). All Craigslist ads, other job boards and social media will have email reply turned off so that potential participants will have to call the study team. Facebook posts will have a link to a PDF of the approved flyer, which will direct any subjects to contact the study team. All content published for both internal and external promotion will utilize the approved flyer or other approved language so that anyone interested in the study will have to call the study team for more information. Newspaper, job board and social media ads will utilize the approved Craigslist ad language unless other language is specifically approved. If potential subjects are referred by their VA providers, the provider will first ask permission from the subject to discuss the research project. If the subject gives permission, the provider will document this either in a CPRS note or encrypted email to the study team. VA providers may also send out our approved flyer with their regular occurring mail outs to their clients.

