Part 2: Visits 3 and 4: Scan Days: All study procedures will happen at the Portland VA except for the MRI scans which will take place at the OHSU AIRC. MA administration and questionnaires may take place at either the VA or OHSU. Subjects are asked to abstain from MA for 72 h before the scan. A urinalysis will be performed to ensure that women are not pregnant and that no other drugs are present. Subjects will undergo a baseline MRI scan approximately 1 hour after the start of each visit followed by drug administration (placebo or MA) and a second scan 1.5 hours after that. Blood samples (3 mL) and/or oral fluid samples will be drawn before drug administration and after the second scan to quantify MA levels. At the Portland VA, during visit 2, up to 15 mL blood will be drawn and a cheek swab will be taken and both will be stored in the MARC biorepository located at the Portland VA. Blood may be stored as plasma or whole blood. Surveys and neurocognitive assessments will be performed before and after each scan at the Portland VA. Pulse, respiration, and pulse oximetry will be monitored throughout each scan. Each visit will last approximately 8 hours, and the subjects will be monitored (blood pressure, heart rate) closely throughout. The Systematic Assessment for Treatment Emergent Effects (SAFTEE) will be used to screen for adverse effects at the end of the day and the individual will be provided with discharge instructions in both verbal and paper form, which informs the subjects that these medications have the potential to impair driving and operation of heavy equipment. Subjects will be given a list of drugs that should be avoided for their interactive potential with MA and will be provided with a phone number to call [name] with questions. A break of at least two days will be required between visits to allow washout. Subjects will be required to take public transit or have a designated driver for each visit. Subjects may be offered a meal from OCTRI nutrition services, snacks or gift card to the VA canteen during each of these visits. Subjects may be asked to be a backup subject for Visits 3 or 4. Double-booking will help ensure the best use of time and resources. If both participants show up for the visit and we do not complete your visit, they will be paid \$50 in prepaid debit cards for your time.

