MA Administration and Randomization: For Part 2, subjects will randomly receive oral MA (0.25 -0.3 mg/kg; Desoxyn®, Lundbeck) on one visit and placebo on the other. Subjects with weight between 50-60 kg, will receive 15 mg oral dose; 60-80 kg, 20 mg; 80-100 kg, 25 mg; 100+ kg to max weight, 30 mg dose. The VA Portland Research pharmacy will provide MA and identical PBO in tablet form. The pharmacy will maintain a randomization schedule such that for each group of 6 subjects, three will receive MA on visit 2 and three will receive MA on visit 3. Study staff will be blinded to treatment.

Weight (kg)	MA Dose (mg)
50 - 60	15
60 - 80	20
80 – 100	25
100 +	30

Appointment Confirmation: Once subjects are consented, appointment confirmation with occur via phone or email. Appointment confirmation emails may be sent via Azure to subjects. Brief scheduling correspondence may also happen through Azure if the study team is not able to connect with the subject via phone. Subjects will be screened for COVID-19 symptoms during confirmation calls prior to study visits and again at the beginning of each in-person visit along with a temperature check. If any symptoms are revealed, the visit will be rescheduled for at least two weeks or until symptoms are resolved.

Subject Reimbursement: Participants will be paid in the form of Clincards for completing all or partial study procedures and will be paid at the end of the visit. For Clincard payments, subjects will be registered by name in the Clincard online system and issued a loaded debit card. Participants will be reimbursed \$40 for the first and second visits, \$100 for the third visit and \$125 for the fourth visit (total = \$305) in the form of prepaid debit cards. Participants who need to combine visits or break visits into multiple sessions will be prorated based on completion of tasks during the session. Subjects will also be offered Trimet day use tickets if they are using public transportation. If both subjects show-up to a double-booked appointment, the subject not undergoing imaging will receive a \$50 prepaid gift card for the inconvenience and be rescheduled. Subjects may be asked to repeat procedures if data isn't usable. If an entire visit is repeated, then they'll be paid for the whole visit at the regular amount again. They will be paid at a pro-rate of \$20/hr for any other repeated procedures or partial visits.

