RSFC time courses will also be normalized and detrended, and signals correlated with motion, mean white matter, mean ventricle and mean brain, along with their temporal derivatives, will be removed through linear regression. Motion regression will include 6 parameter displacement time courses plus their derivatives and squares; only frames where displacement is below standard cutoffs will be included in the regression. Postregression time courses will be band-pass filtered between 0.009 and 0.08 Hz. Signal from ventricular regions and from white matter will be removed from the data through linear regression estimations. Specific Outcome Measures and Hypotheses: We will use a mixed effects model with one between-subjects variable (genotype) to investigate outcome variables. Precision brain mapping (Gordon et al., 2017) allows these analyses to occur between subjects with excellent power. SA 1 and Hy 1 predicts a significant effect of genotype on baseline intrastriatal connectivity and craving. Subsequent analyses can be conducted in several ways based on these data. We will use both a hypothesis driven seed region approach based on a priori region of interests (ROIs) of the VS, midbrain, dorsolateral prefrontal cortex, and ventromedial prefrontal cortex and a data driven approach based on a fcMRI correlation matrix. Bivariate correlations between the average BOLD signals from these regions will provide connectivity estimates. In addition to our planned seed-based comparisons, we will secondarily investigate whole brain connectivity with pair-wise correlations between each ROI within the several sets of functionally-defined parcellations and subcortical ROIs. forming correlation matrices. We use ROIs from the highly cited and utilized Gordon Parcellation (Schaefer et al., 2017;Gordon et al., 2016), a set of 333 ROIs supplemented by a set of 19 subcortical regions defined by FreeSurfer (Fischl, 2012) during pre-processing. Correlations will be Fisher's Z transformed to correct for non-normality and to allow averaging across groups. Sub-matrices will be derived using InfoMap and sub-graphs identified with known cerebral networks (Fortunato and Hric, 2016;Rosvall and Bergstrom, 2008). Correlation matrices will provide access to specific circuits within individuals and will be utilized to describe and provide specific predefined network strengths and characteristics (e.g. default-mode, fronto-parietal, dorsal attention and salience attribution), as well as topological properties for each individual and genotype group. Statistical analysis for these effects are modeled after Feczko et al. (2017) and Eggebrecht et al. (2017) and are detailed in 4.4 Statistical Design and Power. Such an approach allows us to consider individual differences in the functional neuroanatomy, as well as investigate genotype-MA interactions. Topological measures include: connection density and strength, network segregation, global efficiency, rich club coefficients, and global segregation; "hub" measurements will include hub degree, strength, within module z-score, and participation coefficient. SA 2 and Hy 2 predicts a significant genotype x acute drug administration interaction, specifically that acute MA administration will have a blunted effect in the CV group. For Hy 2 and Hy 3 our primary analytic model

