
will again be a linear mixed effects analysis, with two within-subjects factors (scan day and drug) with either RSFC or behavioral measures included as dependent variables and main effects of genotype and their interaction as primary predictors. Post-hoc analyses will be used as necessary to examine effects for individual outcomes and to estimate allelic frequency associations as well as sex by genotype interactions. **HY 3** would be confirmed by finding a blunted effect of MA administration on reports of euphoria and craving and on effects on attention and cognitive control in the CV group.

Interpretation of Results: Higher RSFC in CV vs. WT would be consistent with our hypothesis that neuroadaptations to *chronic* MA use interact with genotype to differentially alter striatal connectivity. A blunted effect of *acute* MA on RSFC in CV vs. WT groups would be consistent with our hypothesis that the CV, v288v, is associated with increased TAAR1 signaling that diminishes the corticostriatal effects of MA. The lack of group differences would suggest that genotype does not moderate the MA effects and opposing results may indicate compensatory mechanisms in those with the *htaar1* variant.

Risks to Subjects

All study data derived from subject procedures (including tasks, rating scales, screening interview questionnaires and MRI scan) are obtained specifically for research purposes and not for treatment. Urine and blood specimens will be analyzed by the VA lab and destroyed according to protocol. UAs will be obtained and analyzed by the research team or the VA lab and will be destroyed according to protocol. Two cheek swabs will be taken, the first will be analyzed for genotype and then destroyed. The second will be taken during Visit 2 and banked for future research. MRI scans are obtained at the Advanced Imaging Research Center at OHSU and stored on a disk partition specific to this study and only accessible by study staff. The imaging data are downloaded to image analysis workstations located in the [name] Lab at the VA and raw images are archived on a dedicated server at the OHSU Advanced Computing Center (ACC). Coded data may be processed temporarily on additional OHSU servers in the future.

Risks of Questionnaires, Computer Tasks and Cognitive/Neuropsychological Testing: Participants may become upset or frustrated while answering personal questions during the interview or during administration of the neuropsychological tests

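### The primary Hy 2/Hy 3 model does not say how the pre-dose measurements from the two dosing days enter; adjusting genotype x drug for them is a cheap improvement.

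*Combined protocol and SAP*

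**What the plan says.** Under *Part 2: Visits 3 and 4: Scan Days* the protocol states: "Subjects will undergo a baseline MRI scan approximately 1 hour after the start of each visit followed by drug administration (placebo or MA"). The post-dose scan is then described as follows: "and a second scan 1.5 hours after that". The same section adds: "Surveys and neurocognitive assessments will be performed before and after each scan". Under *MA Administration and Randomization*, MA is given "on one visit and placebo on the other". Each completer therefore has four scans, two of them pre-dose, with behavioural scores alongside.

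Under *Specific Outcome Measures and Hypotheses*, the Hy 2/Hy 3 model is a linear mixed model "with two within-subjects factors (scan day and drug) with either RSFC or behavioral measures included as dependent variables", with genotype and its interaction as primary predictors. It names no pre/post term, baseline covariate or change score, and gives no rule for coding drug on a pre-dose scan.

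Baseline has an explicit analytic role only in Hy 1: "SA 1 and Hy 1 predicts a significant effect of genotype on baseline intrastriatal connectivity and craving". The hypotheses follow the same split. Hypothesis 1 points to the base panel of Figure 1C, and Hypothesis 2 predicts a fall "with a blunted decrease in the CV group (Figure 1C: MA and PBO").

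For statistical detail the plan refers to a section 4.4, which is not in the supplied text.

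**The concern.** Genotype x drug is the test of both Hy 2 and Hy 3, with 18 CV and 18 WT completers planned among the MUD participants. A measurement taken a few hours earlier on the same day can remove day-to-day variation from the MA-minus-placebo difference. These measurements are already being collected on both days, yet the model statement does not say whether or how they are used.

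The wording admits more than one implementation, and these differ in precision. At this sample size the choice matters, and it should be made before the data are seen.

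**Working it through.** **Inputs from the documents.** There are four groups of 18 (4 x 18 = 72), so the MUD comparison is 18 v 18. Treatment order is balanced three and three in each six, with stratification by genotype. Washout is at least two days. The plan gives no effect size, SD, correlation, alpha or numeric power, so there is no power figure to reproduce.

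**Assumptions.** Two-sided 0.05; a true genotype difference of 0.8 SD of the post-dose MA-minus-placebo difference; unit variances; between-day correlation rb of 0.4-0.6; within-day pre/post correlation rw of 0.6-0.8. Participants added from the MARC biorepository are not counted; they would raise power with or without adjustment.

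**Formulas.** Let D1 be the post-dose MA-minus-placebo difference and D0 the same difference of pre-dose values.
- Var(D1) = Var(D0) = 2(1 - rb) and Cov(D1, D0) = 2(rw - rb), so r = corr(D1, D0) = (rw - rb)/(1 - rb).
- Post-dose only, with sequence: noncentrality 0.8 x sqrt(18/2) = 2.4 on 33 df, giving 64% power.
- Adjusted for D0 and sequence: variance factor (1 - r²)(1 + 1/31), where the second term is the cost of estimating the slope. Noncentrality is 2.4/sqrt(factor) on 32 df.
- Change score D1 - D0: variance factor 2(1 - r), which exceeds 1 when r < 0.5. Noncentrality is 2.4/sqrt(factor) on 33 df.

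Example at rb/rw = 0.5/0.7: r = 0.2/0.5 = 0.4; 1 - r² = 0.84; 0.84 x 1.032 = 0.867; 2.4/sqrt(0.867) = 2.58; power about 71%.

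| rb/rw | r | Variance reduction | Post-dose only | Adjusted | Change score |
|---|---|---|---|---|---|
| 0.4/0.6 | 0.33 | 11% | 64% | 68% | 52% |
| 0.4/0.7 | 0.50 | 25% | 64% | 75% | 64% |
| 0.4/0.8 | 0.67 | 44% | 64% | 87% | 81% |
| 0.5/0.6 | 0.20 | 4% | 64% | 65% | 45% |
| 0.5/0.7 | 0.40 | 16% | 64% | 71% | 57% |
| 0.5/0.8 | 0.60 | 36% | 64% | 82% | 74% |
| 0.6/0.6 | 0 | 0% | 64% | 63% | 38% |
| 0.6/0.7 | 0.25 | 6% | 64% | 66% | 48% |
| 0.6/0.8 | 0.50 | 25% | 64% | 75% | 64% |

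Simulation with sequence in the model (20,000 runs per case) gave adjusted power within about one point of these values. Both the post-dose and the adjusted estimates averaged the true effect.

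**If MA weakens the within-day correlation.** With separate placebo-day (rp) and MA-day (rm) correlations, r = (rp + rm - 2rb)/(2(1 - rb)).
- rb 0.5, rp 0.7, rm 0.5: r = 0.2/1.0 = 0.2, reduction 4%, power 65%.
- rb 0.5, rp 0.7, rm 0.4: r = 0.1, reduction 1%, power 63%.
- rb 0.6, rp 0.7, rm 0.5: r = 0, no reduction, power 63%.

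**Coding safeguard.** If all four scans entered with drug coded by the day's treatment, the contrast would be (D1 + D0)/2. D0 carries no drug effect, so the expected estimate is half the true one: 0.50 would be estimated as 0.25.

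**The case against.** The strongest reply is that the pre-dose values may already be in the model. The description of Specific Aim 1 says that genotype and drug-by-genotype effects will be studied both at baseline and after MA. Two within-subject factors can also be read as day by pre/post, which accounts for all four scans. Section 4.4 may settle the matter. This stands to the extent that the role of the pre-dose values is unstated, and a reader should not infer that the plan gives them none. It does not remove the point: day by pre/post is in effect a change score, and its power is below the adjusted analysis in all nine cases above.

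The second reply is that a post-dose crossover contrast is valid, because order is balanced and stratified by genotype. That stands in full. Adjustment buys precision only, and baseline adjustment in a crossover is optional.

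The third is that the gain rests on assumed correlations. That also stands. The 87% figure is the most favourable of nine cases, and the gain can vanish if MA alters the pre/post relation, which is plausible given that Hy 2 expects MA to change connectivity.

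A reader might go further and infer that the plan will halve its own estimate by labelling pre-dose scans with the day's treatment. The documents do not support that. No passage says that it would be done, and the protocol itself calls the first scan of each visit a baseline.

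**Conclusion.** The point holds as a cheap improvement and a needed clarification; no bias is shown. The available text does not state how pre-dose values enter the Hy 2/Hy 3 model. Of the two natural readings, one leaves the same-day baseline unused and the other uses it in a form less precise than post-dose only when r is below 0.5.

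Under the assumed correlations, covariate adjustment moves power from 64% to about 63-75% in seven of the nine cases. It reaches 82-87% only when the within-day correlation is 0.8 and the between-day correlation is 0.5 or lower. If MA lowers the within-day correlation on the MA day, there is essentially no gain. The conclusion is limited to the supplied text, since section 4.4 could not be read.

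**What to change.** State the Hy 2/Hy 3 model as follows, or bring equivalent wording across from section 4.4.

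- **Outcome and terms:** the post-dose value, with visit, treatment, genotype and genotype x treatment; the last is the test. Adjust for the same-visit pre-dose value and the subject-mean pre-dose value. With complete data this equals analysing the post-dose MA-minus-placebo difference adjusted for the pre-dose difference and sequence.
- **Coding:** pre-dose values are not coded with the day's treatment. This is a safeguard only.
- **Behavioural scores:** use the same form for craving, subjective and cognitive measures. Name the single pre-dose assessment that serves as baseline for each, since they are taken more than once before dosing.
- **Carryover check:** compare pre-dose values by treatment order. The second visit's baseline follows the first treatment after as little as two days, and any carryover would enter the adjustment.

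The cost is analysis wording, one or two degrees of freedom, and at worst about one point of power. No new data are needed.
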